## APPENDIX 2: Self-Completed HIV Symptom Index (HIV-SI)

**Self-completed HIV Symptom Index**

INSTRUCTIONS: The following questions ask about symptoms you might have had during the past four weeks.

Please answer the following questions by placing a checkmark in the appropriate box.

Symptom	Did not have this symptom	Symptom did not bother me	Symptom bothers me a little	Symptom bothers me	Symptom bothers me a lot
Fatigue or loss of energy					
Fevers, chills or sweats					
Feeling dizzy or lightheaded					
Pain, numbness or tingling in the hands or feet					
Trouble remembering					
Nausea or vomiting					
Diarrhea or loose bowel movements					
Felt sad, down, or depressed					
Felt nervous or anxious					
Difficulty falling or staying asleep					
Skin problems, such as rash, dryness or itching					
Cough or trouble catching your breath					
Headache					
Loss of appetite or a change in the taste of food					
Bloating, pain, or gas in your stomach					
Muscle aches or joint pain					
Problems with having sex, such as loss of interest or lack of satisfaction					
Changes in the way your body looks such as fat deposits or weight gain					
Problems with weight loss or wasting					
Hair loss or changes in the way your hair looks					

## APPENDIX 3: Exhibit B, Safety and Data Collection and Reporting

**EXHIBIT B****Requirements for Safety Data Collection and Reporting****1. OVERVIEW**

As the sponsor of the Study, INSTITUTION and PRINCIPAL INVESTIGATOR shall be solely responsible for complying, within the required timelines, any safety reporting obligation to competent Health Authorities, IRB/ECs and any participating (co or sub) investigators, as defined in applicable laws and regulations. For the purposes of this EXHIBIT, safety data includes adverse events, product quality complaints (PQCs), and special situations including pregnancies.

The INSTITUTION and PRINCIPAL INVESTIGATOR will provide safety information to the COMPANY on adverse events, special situations including pregnancies and product quality complaints as defined within this EXHIBIT.

**2. Management of Safety Data**

This Study has been designated as an interventional study. As such, all adverse events, special situations including pregnancies and product quality complaints will be reported as described in this exhibit from the time a subject has signed and dated an Informed Consent Form (ICF) until 30 days after the last documented use of a product under study within the study.

For the purposes of this study, the J&J medicinal product is: Symtuza

**3. Definitions****3.1. Adverse Event (AE)**

An adverse event is any untoward medical occurrence in a clinical study subject administered a medicinal (investigational or non-investigational) product. An adverse event does not necessarily have a causal relationship with the treatment. An adverse event can therefore be any unfavorable and unintended sign (including an abnormal finding), symptom, or disease temporally associated with the use of a medicinal (investigational or non-investigational) product, whether or not related to that medicinal (investigational or non-investigational) product. (Definition per International Conference on Harmonization [ICH])

This includes any occurrence that is new in onset or aggravated in severity or frequency from the baseline condition, or abnormal results of diagnostic procedures, including laboratory test abnormalities.

**3.2. Adverse Events of Special Interest**

Adverse events of special interest are events that the COMPANY is actively monitoring as a result of a previously identified signal (even if non-serious). No adverse events of special interest will be collected for this study.

**3.3. Individual Case Safety Report (ICSR)**

A valid ICSR must contain the four minimum criteria required to meet regulatory reporting requirements.

- an identifiable subject (but not disclosing personal information such as the subject's name, initials or address)
- an identifiable reporter (investigational site)
- a J&J medicinal product
- an adverse event, outcome, or certain special situations

The minimum information required is:

- suspected J&J medicinal product (doses, indication)
- date of therapy (start and end date, if available)
- batch or lot number, if available
- subject details (subject ID and country)
- gender
- age at AE onset

## APPENDIX 3: Exhibit B, Safety and Data Collection and Reporting

- reporter ID
- adverse event detail (AE verbatim in English), onset date, relatedness, causality, action taken, outcome, (if available)
- J&J protocol ID

**3.4. Product Quality Complaint (PQC)**

A product quality compliant is defined as any suspicion of a product defect related to a potential quality issue during manufacturing, packaging, release testing, stability monitoring, dose preparation, storage or distribution of the product, or delivery system. Not all PQCs involve a subject. Lot and batch numbers are of high significance and need to be collected whenever available.

Examples of PQC include but not limited to:

- Functional Problem: e.g., altered delivery rate in a controlled release product
- Physical Defect: e.g. abnormal odor, broken or crushed tablets/capsules
- Potential Dosing Device Malfunction: e.g., autoinjector button not working, needle detaching from syringe
- Suspected Contamination
- Suspected Counterfeit

**3.5. Serious Adverse Event (SAE)**

A serious adverse event based on ICH and EU Guidelines on Pharmacovigilance for Medicinal Products for Human Use is any untoward medical occurrence that at any dose:

- Results in death
- Is life-threatening  
(The subject was at risk of death at the time of the event. It does not refer to an event that hypothetically might have caused death if it were more severe.)
- Requires inpatient hospitalization or prolongation of existing hospitalization
- Results in persistent or significant disability/incapacity
- Is a congenital anomaly/birth defect
- Is a suspected transmission of any infectious agent via a medicinal product
- Is medically important\*

\*Medical and scientific judgment should be exercised in deciding whether expedited reporting is also appropriate in other situations, such as important medical events that may not be immediately life threatening or result in death or hospitalization but may jeopardize the subject or may require intervention to prevent one of the other outcomes listed in the definition above. These should usually be considered serious.

**NOTE: DEATH FOR ANY REASON SHOULD BE REPORTED AS A SERIOUS ADVERSE EVENT.**

**3.5.1. Hospitalization**

For reports of hospitalization, it is the sign, symptom or diagnosis which led to the hospitalization that is the serious event for which details must be provided.

Any event requiring hospitalization or prolongation of hospitalization that occurs during the study must be reported as a serious adverse event, except hospitalizations for the following:

- Hospitalizations not intended to treat an acute illness or adverse event (e.g., social reasons such as pending placement in long-term care facility)
- Surgery or procedure planned before entry into the study. [Note: Hospitalizations that were planned before the start of data collection and where the underlying condition for which the hospitalization

## APPENDIX 3: Exhibit B, Safety and Data Collection and Reporting

was planned has not worsened will not be considered serious adverse events. Any adverse event that results in a prolongation of the originally planned hospitalization is to be reported as a new serious adverse event.]

**3.5.2. Life-Threatening Conditions**

The cause of death of a subject in a study 30 days of the last dose of study drug, whether or not the event is expected or associated with the study drug, is considered a serious adverse event.

**4. Unlisted (Unexpected) Adverse Event/Reference Safety Information**

An adverse event is considered unlisted if the nature or severity is not consistent with the applicable product reference safety information. For a medicinal product(s) with a marketing authorization, the expectedness of an adverse event will be determined by whether or not it is listed in the applicable product information. <https://www.symtuza.com/>

**5. Special Reporting Situations**

Safety events of interest for a J&J medicinal product that require expediting reporting and/or safety evaluation include, but are not limited to:

- Drug exposure during pregnancy (maternal and paternal)
- Overdose of a J&J medicinal product
- Exposure to a J&J medicinal product from breastfeeding
- Suspected abuse/misuse of a J&J medicinal product
- Inadvertent or accidental exposure to a J&J medicinal product
- Medication error (includes potential, intercepted or actual) involving a J&J product (with or without patient exposure to the J&J Product(s) Under Study, e.g., name confusion)
- 
- Suspected transmission of any infectious agent via administration of a medicinal product
- Unexpected therapeutic or clinical benefit from use of a J&J medicinal product
- Any failure of expected pharmacological action (i.e., lack of effect) of a J&J medicinal product

These safety events may not meet the definition of an adverse event; however, from a COMPANY perspective, they are treated in the same manner as adverse events. Special situations should be recorded on the Adverse Event page of the CRF.

Any special situation that meets the criteria of a serious adverse event should be recorded on a Serious Adverse Event Report Form and be reported to the COMPANY **within 24 hours of becoming aware of the event.**

**6. Pregnancy**

All initial reports of pregnancy must be reported to the COMPANY by the PRINCIPAL INVESTIGATOR **within 24 hours of becoming aware of the event** using the Serious Adverse Event Form. Abnormal pregnancy outcomes (e.g. spontaneous abortion, fetal death, stillbirth, congenital anomaly, ectopic pregnancy) are considered serious adverse events and must be reported using the Serious Adverse Event Form.

Any subject who becomes pregnant during the study must be promptly withdrawn from the study and discontinue further study treatment.

Because the effect of the J&J medicinal product on sperm is unknown, pregnancies in partners of male subjects exposed to a J&J medicinal product will be reported by the PRINCIPAL INVESTIGATOR **within 24 hours of their knowledge of the event** using the Serious Adverse Event Form. Depending on local legislation this may require prior consent of the partner.

Follow-up information regarding the outcome of the pregnancy and any postnatal sequelae in the infant will be required.

## APPENDIX 3: Exhibit B, Safety and Data Collection and Reporting

**7. Maintenance of Safety Information**

All safety data should be maintained in a clinical database in a retrievable format. The INSTITUTION and PRINCIPAL INVESTIGATOR shall provide all adverse events, both serious and non-serious, in report format. However, in certain circumstances more frequent provision of safety data may be necessary, e.g. to fulfill a regulatory request, and as such the data shall be made available within a reasonable timeframe at the COMPANY's request.

**8. Procedures for Reporting Safety Data and Product Quality Complaints (PQCs) for J&J Medicinal Products to the COMPANY**

All adverse events and special situations, whether serious or non-serious, related or not related, following exposure to a J&J medicinal product are to be documented by the investigator and recorded in the CRF and in the subject's source records. Investigators must record in the CRF their opinion concerning the relationship of the adverse event to a J&J medicinal product.

All (serious and non-serious) adverse events reported for a J&J medicinal product should be followed-up in accordance with clinical practice.

**8.1. SAEs, Adverse Events of Special Interest and Special Reporting Situations**

All serious adverse events that have not resolved by the end of the study, or that have not resolved upon discontinuation of the subject's participation in the study, must be followed until any of the following occurs:

- The event resolves
- The event stabilizes
- The event returns to baseline, if a baseline value/status is available
- The event can be attributed to agents other than the study drug or to factors unrelated to study conduct
- It becomes unlikely that any additional information can be obtained (subject or health care practitioner refusal to provide additional information, lost to follow-up after demonstration of due diligence with follow-up efforts)

The INSTITUTION and the PRINCIPAL INVESTIGATOR will transmit all SAEs, Adverse Events of Special Interest and special situations following exposure to a J&J product under study in a form provided by the COMPANY in accordance with Section 9, Transmission Methods, in English within 24-hours of becoming aware of the event(s).

In the event the study is blinded, the PRINCIPAL INVESTIGATOR will submit an unblinded SAE or pregnancy exposure report to COMPANY.

All follow-up information for serious adverse events that are not resolved at the end of the study or by the time of patient withdrawal must be reported directly by the PRINCIPAL INVESTIGATOR, within 24 hours becoming aware, to the COMPANY using the COMPANY's Serious Adverse Event Report

All available clinical information relevant to the evaluation of a related SAE, Adverse Events of Special Interest, serious ADR or special situation is required.

- The INSTITUTION and/or PRINCIPAL INVESTIGATOR is responsible for ensuring that these cases are complete and if not are promptly followed-up. A safety report is not considered complete until all clinical details needed to interpret the case are received. Reporting of follow-up information should follow the same timeline as initial reports.

## APPENDIX 3: Exhibit B, Safety and Data Collection and Reporting

- Copies of any and all relevant extraordinary (not including routine initial or follow-up ICSR submission) correspondences with regulatory authorities and ethics committees regarding any and all serious adverse irrespective of association with the J&J Product under study, are to be provided to the COMPANY using a transmission method in Section 9 within 24 hours of such report or correspondence being sent to applicable health authorities.

**8.2. Non-Serious AEs**

All non-serious adverse events should be reported to COMPANY according to the timeframe outlined in the Research Funding Agreement section entitled Reporting of Data.

**8.3. PQC Reporting**

A PQC may have an impact on the safety and efficacy of the product. Timely, accurate, and complete reporting and analysis of PQC information from studies are crucial for the protection of patients, investigators, and the COMPANY, and are mandated by regulatory agencies worldwide. The COMPANY has established procedures in conformity with regulatory requirements worldwide to ensure appropriate reporting of PQC information. Lot and/or Batch #s shall be collected or any reports failure of expected pharmacological action (i.e., lack of effect). The product should be quarantined immediately and if possible, take a picture.

All initial PQCs involving a J&J medicinal product under study must be reported to the COMPANY by the PRINCIPAL INVESTIGATOR within 24 hours after being made aware of the event. The J&J contact will provide additional information/form to be completed.

If the defect for a J&J medicinal product under study is combined with either a serious adverse event or non-serious adverse event, the PRINCIPAL INVESTIGATOR must report the PQC to the COMPANY according to the serious adverse event reporting timelines. A sample of the suspected product should be maintained for further investigation if requested by the COMPANY.

**9. Reporting Procedures for Reporting Safety Data and Product Quality Complaints (PQCs) for Non-J&J Medicinal Products**

For SAEs, special reporting situations and PQCs following exposure to a non-J&J medicinal product under study, the PRINCIPAL INVESTIGATOR should notify the appropriate regulatory/competent authority or the manufacturer of that medicinal product (in the absence of appropriate local legislation) as soon as possible.

**10. Transmission Methods**

The following methods are acceptable for transmission of safety information to the COMPANY:

- Electronically via Janssen SECURE Email service (preferred)
- For business continuity purposes, if SECURE Email is non-functional:
  - Facsimile (fax), receipt of which is evidenced in a successful fax transmission report
- Telephone (if fax is non-functional).

Please use the contact information and process information provided by the COMPANY.

**11. SAEs Listing**

At a minimum, on a semi-annual basis and at the end of the Study, COMPANY will provide to the INSTITUTION and/or PRINCIPAL INVESTIGATOR, a listing of all SAEs reported to the COMPANY. SPONSOR and/or PRINCIPAL INVESTIGATOR will review this listing and will resolve any discrepancies with the data provided by the COMPANY.

**12. Dissemination of Safety Information from COMPANY to INSTITUTION/PRINCIPAL INVESTIGATORS**

## APPENDIX 3: Exhibit B, Safety and Data Collection and Reporting

PRINCIPAL INVESTIGATOR will be responsible for submitting IND safety reports for the Study Product to INSTITUTION's IRB in accordance with Federal regulations 21 CFR 312.66. The PRINCIPAL INVESTIGATOR will provide a copy of each IND safety report to sub-investigators where the study design is either a multi-center or cooperative study.

COMPANY agrees to provide to the PRINCIPAL INVESTIGATOR IND safety reports for the J&J Medicinal Product as they become available until all subjects in the Protocol have completed their last Study visit according to the Protocol (i.e. Last Subject Last Visit has occurred).

**13. Contacting COMPANY Regarding Safety**

The names (and corresponding contact information) of the individuals who should be contacted regarding safety issues will be provided separately by the COMPANY.

## APPENDIX 4 GRADING SCALE FOR SEVERITY OF ADVERSE EVENTS AND LABORATORY ABNORMALITIES

Laboratory Tests	Grade 1	Grade 2	Grade 3	Grade 4
Hemoglobin	8.5-10.0	7.5-8.49	6.5-7.49	<6.5
ANC	1000-1300	750-999	500-749	<500
Platelets	100-125	50-99	25-49	<25
WBC	2.0-2.5	1.5-1.99	1.0-1.49	<1
Hyponatremia	>130	125-129	121-124	<121
Hypernatremia	<150	150-154	154-159	>159
Hypokalemia	>3	2.5-3.0	2.0-2.49	<2.0
Hyperkalemia	5.6-6.0	6.01-6.5	6.51-7.0	>7.0
Hypoglycemia	55-64	40-54.9	30-39.9	<30
Hyperglycemia, Fasting	110-125	126-250	251-500	>500
Hypocalcemia (corrected)	Below normal but above 7.8	7.0-7.8	6.1-6.9	<6.1
Hypercalcemia (corrected)	Above normal but below 11.5	11.5-12.5	12.6-13.5	>13.5
Total Bilirubin	Up to 1.5 x ULN	1.5-2.5 x ULN	2.5-5.0 x ULN	>5.0 x ULN
BUN	1.25-2.5 x ULN	2.6-5.0 x ULN	5.1-10 x ULN	>10 x ULN
Creatinine	1.5-2.0	2.01-3.00	3.01-6.00	>6.00
Bicarb	16-LLN	11-15.9	8-10.9	<8.0
Triglycerides (fasting)	NA	500-750	751-1200	>1200
LDL (fasting)	130-160	161-190	>190	NA
CK	3-6 x ULN	6.1-10 x ULN	10.1-20 ULN	>20 x ULN
AST	1.25-2.5 x ULN	2.6-5.0 x ULN	5.1-10 x ULN	>10 x ULN
ALT	1.25-2.5 x ULN	2.6-5.0 x ULN	5.1-10 x ULN	>10 x ULN
GGT	1.25-2.5 x ULN	2.6-5.0 x ULN	5.1-10 x ULN	>10 x ULN
Alk Phos	1.25-2.5 x ULN	2.6-5.0 x ULN	5.1-10 x ULN	>10 x ULN
Lipase	1.0-1.5 x ULN	1.51-3.0 x ULN	3.01-5.0 x ULN	>5.0 x ULN
Albumin	NA	2.0 to <LLN	<2.0	NA
Hematuria	>ULN-10	>10-75	>75	NA
Proteinuria	1+	2-3+	4+	NA
Glycosuria	1+	2-3+	4+	NA
Cardiac Arrhythmia	Asymptomatic and no intervention indicated	Asymptomatic and non-urgent intervention indicated	Symptomatic and non-urgent intervention indicated	Life threatening or urgent intervention indicated
Cardiac ischemia/infarct	NA	NA	Stable angina or testing with ischemia	Unstable angina or acute MI
Hemorrhage	NA	Symptomatic, no transfusion indicated	Symptomatic, ≤ 2 units PRBC's transfusion indicated	Life threatening or > 2 units PRBC's transfusion indicated
Hypertension	Systolic: 140-159 Diastolic: 90-99	Systolic: 160-179 Diastolic: 100-109	Systolic: >179 Diastolic: 110	Life threatening (i.e. malignant hypertension) or requiring hospital admission
Hypotension	NA	Symptomatic, corrected with oral fluids	Symptomatic, IV fluids indicated	Refractory shock

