### 7.6. Toxicity Management

7.6.1. All clinical events and clinically significant laboratory toxicities will be managed according to uniform guidelines detailed in Appendix 3 and as outlined below.

7.6.1.1. Clinical events and clinically significant laboratory abnormalities will be graded according to the Grading Scale for Severity of Adverse Events and laboratory Abnormalities (Appendix 4).

7.6.1.2. Grade 3 and 4 clinically significant laboratory abnormalities should be confirmed by repeat testing within 5 calendar days of receiving results and before study drug discontinuation, unless such a delay is not consistent with good medical practice.

7.6.1.3. Any questions regarding toxicity management should be directed to the Investigator.

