## APPENDIX 4: Grading Scale for Severity of Adverse Events and Laboratory Abnormalities

Osteonecrosis	NA	Asymptomatic but with radiologic findings and no surgical intervention indicated	symptomatic with radiologic findings or surgical intervention indicated	Disabling bone pain with radiologic findings causing inability to care for self
Acute systemic allergic reaction	Localized urticaria with no medical intervention indicated	Localized urticaria with mild angioedema with no medical intervention indicated	Gen urticaria or angioedema with medical intervention indicated or bronchospasm	Anaphylaxis, laryngeal angioedema, laryngeal edema or life-threatening bronchospasm
Chills	without impact on activities	moderate, with impact on activities	severe, unable to perform typical activities	NA
Fatigue/malaise	without impact on activities	moderate, with impact on activities	severe, unable to perform typical activities	Incapacitating symptoms, unable to perform basic self-care
Fever	99.8-101.5	101.6-102.8	102.9-104.9	>104.9
Pain	without impact on activities	moderate, with impact on activities	severe, unable to perform typical activities	Incapacitating symptoms, unable to perform basic self-care
Unintentional weight loss	NA	5-9% loss of body weight	10-19% loss of body weight	>19% loss of body weight or aggressive intervention indicated (feeding tube, TPN)
Lipodystrophy or lipoatrophy	detectable by subject	Detectable by provider	Obvious or disfiguring	NA
Diabetes mellitus (new onset)	NA	without indication for medications	Medications indicated	Life threatening consequences
Diabetes mellitus (existing)	NA	Requiring modification of medications	Lack of control despite medication modification	Life threatening consequences
Gynecomastia	detectable by subject	Detectable by provider	Obvious or disfiguring	NA
Hyperthyroidism	asymptomatic	Symptoms causing moderate impact of activities OR medication indicated	Symptoms causing inability to perform activities OR medication indicated	Life threatening consequences
Hypothyroidism	asymptomatic	Symptoms causing moderate impact of activities OR medication indicated	Symptoms causing inability to perform activities OR uncontrolled despite medication	Life threatening consequences
Intermenstrual bleeding	Spotting	≤ typical menstrual cycle	≥ typical menstrual cycle	Hemorrhage with life threatening hypotension

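### Several Appendix 4 bands do not give one grade per value, and some of these points lie on the Grade 2/3 line that governs study drug (minor)

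*Protocol*

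**What the plan says.** Section 7.6.1.1 makes Appendix 4 the operative scale: "Clinical events and clinically significant laboratory abnormalities will be graded according to the Grading Scale for Severity of Adverse Events". Section 8.3.2.1 adds that laboratory toxicity is re-graded in the analysis dataset according to the protocol.

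The rows at issue, with cells in order from Grade 1 to Grade 4:

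- Bilirubin: "Total Bilirubin Up to 1.5 x ULN 1.5-2.5 x ULN 2.5-5.0 x ULN >5.0 x ULN"
- High sodium: "Hypernatremia <150 150-154 154-159 >159"
- Low sodium: "Hyponatremia >130 125-129 121-124 <121"
- BUN, AST, ALT, GGT and alkaline phosphatase share one set of bands: 1.25-2.5, 2.6-5.0, 5.1-10 and >10 x ULN.
- Hyperthyroidism Grade 3: "Symptoms causing inability to perform activities OR medication indicated". The need for medication is also an alternative criterion in Grade 2 of that row.
- Intermenstrual bleeding, Grades 2 and 3: "≤ typical menstrual cycle ≥ typical menstrual cycle"

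The grade then sets the action. Grades 1 and 2 are handled alike, at the investigator's discretion (7.6.2.1). Clinically significant Grade 3 and 4 laboratory abnormalities are to be repeated within 5 calendar days (7.6.1.2). A related Grade 3 means withholding until Grade 2 or lower (7.6.3.2). A related laboratory abnormality that returns to Grade 3 or higher on re-challenge means permanent discontinuation (7.6.3.3).

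**The concern.** A grading scale used for dosing decisions has to return exactly one grade for each abnormal value. Here some values return two and some return none, and the protocol gives neither a tie-break nor a rounding rule.

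Most is at stake on the Grade 2/3 line. At such a value it is unclear whether the 5-day repeat test is called for, whether a withheld subject may restart, and whether a recurrence after re-challenge ends treatment. Two staff members could apply the table correctly and act differently, and a program that re-grades the data could differ from both. On the Grade 1/2 line only the tabulated grade changes.

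**Working it through.** There is no stated figure to reproduce. The check is whether each printed row maps each value to one grade.

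**Method.** Each band is read as printed: a-b includes both ends, > and < exclude the limit, and an upper-limit-only cell includes that limit. Each of the 26 numeric laboratory rows (the two dipstick rows are left out) is scanned at the finest step that its own limits show: 1 for sodium, 0.1 for bilirubin, and 0.01 for the five rows that print 1.25.

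**Result.** Eight of the 26 rows have a value with two grades or none.

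| Row | Value | Grades returned | Line affected |
|---|---|---|---|
| Hypernatremia | 154 | 2 and 3 | 2/3 |
| Total bilirubin | 2.5 x ULN | 2 and 3 | 2/3 |
| Total bilirubin | 1.5 x ULN | 1 and 2 | 1/2 |
| Hyponatremia | 130 | none (129 is Grade 2, 131 is Grade 1) | 1/2 |
| BUN, AST, ALT, GGT, alkaline phosphatase | 2.51-2.59 x ULN | none | 1/2 |
| The same five rows | 5.01-5.09 x ULN | none | 2/3 |

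**The gaps in reportable units.** The protocol states no ULN, so these are assumptions.

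- ALT, ULN 40 U/L: 2.5 x 40 = 100 and 2.6 x 40 = 104, so 101-103 have no grade. 5.0 x 40 = 200 and 5.1 x 40 = 204, so 201-203 have none.
- ALT, ULN 50 U/L: 126-129 and 251-254 have no grade, by the same arithmetic.
- Rounding the ratio to 0.1 closes both gaps. The protocol does not say to round, and a ratio rounded to 0.1 cannot express the printed lower limit of 1.25.

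**The bilirubin tie in reportable units.** With ULN assumed at 1.0, 1.1, 1.2 and 1.3 mg/dL, 2.5 x ULN is 2.50, 2.75, 3.00 and 3.25 mg/dL. If results are reported to 0.1, the exact tie occurs at 2.5 mg/dL (ULN 1.0) and 3.0 mg/dL (ULN 1.2), and not at all at ULN 1.1 or 1.3. If the ratio is rounded to 0.1, the tie covers 2.7-2.8 mg/dL at ULN 1.1 and 3.2-3.3 mg/dL at ULN 1.3.

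**Clinical rows.** A hyperthyroid subject who needs medication meets Grade 2 and Grade 3. The hypothyroidism row shows how the grades can be separated, since its Grade 3 reads "Symptoms causing inability to perform activities OR uncontrolled despite medication". Bleeding equal to a typical cycle meets Grade 2 and Grade 3 because both cells include equality.

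**Consequence by line.**

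- Laboratory values on the 2/3 line touch 7.6.1.2, 7.6.3.2 and 7.6.3.3. With bilirubin at exactly 2.5 x ULN, for example, the restart condition (Grade 2 or lower) is met while the value is still Grade 3. After re-challenge, the same value both is and is not a recurrence.
- The two clinical rows touch withholding and restart (7.6.3.2) only, because 7.6.1.2 and 7.6.3.3 concern laboratory abnormalities.
- Points on the 1/2 line change no action, because 7.6.2.1 treats Grades 1 and 2 alike.

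**The case against.** The strongest reply is that this is editorial. Withholding drug at a tied value satisfies both the Grade 2 rule, which leaves continuation to discretion, and the Grade 3 rule. Section 7.6.1.3 sends toxicity questions to the investigator, and the clinic sample comes from a single site. Section 7.5.1.1 grades an adverse event tied to a laboratory abnormality on clinical severity, which may differ from the laboratory grade. A tie-break or rounding rule for the re-graded dataset may also stand in the SAP, which is not at hand.

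Much of this stands. A reader might infer that the protocol orders continuation and withholding at once. It does not, because withholding breaks neither rule. The reply does not settle restart or recurrence after re-challenge, where the two grades lead to different outcomes. Nor can a rule in the SAP help staff who grade in real time from Appendix 4, and 8.3.2.1 itself points back to the protocol.

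A reader might also infer that normal bilirubin is Grade 1, because that cell has no lower limit while hypocalcemia, for instance, is anchored at normal ("Below normal but above 7.8"). That is too literal: the scale is for abnormalities, and 7.6.1.1 grades only clinically significant ones. A stated lower limit would be a clarification, not the repair of an error.

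**Conclusion.** The point holds and is minor. Eight of 26 numeric laboratory rows and two clinical rows fail to give one grade per value. The points that can change management are sodium 154, bilirubin 2.5 x ULN, 5.01-5.09 x ULN in the five shared-band rows, and the two clinical overlaps. The rest affect only the recorded grade.

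The five-row gap depends on reading ratios at 0.01, the finest step those rows print; at 0.1 it disappears. The sodium and bilirubin faults do not depend on this. The examples in reportable units rest on assumed ULNs.

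The affected values are single points or narrow ranges, and withholding also requires that the abnormality be clinically significant, confirmed and related. The protocol gives no basis for a frequency; with a target of 30 subjects, such values should be rare.

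A reader might infer that endpoint 4.2.2.3 is compromised, since it covers AST and ALT and those rows have gaps. The documents do not support this: 4.2.2.3 refers to significant changes and does not cite Appendix 4 grades. The discontinuation count (4.2.2.6) could be reached through 7.6.3.3, but only indirectly and improbably. The primary endpoint is not involved.

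**What to change.** Amend these cells of Appendix 4:

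- Bilirubin: Grade 1 >ULN to 1.5, Grade 2 >1.5 to 2.5, Grade 3 >2.5 to 5.0 x ULN. The Grade 1 lower limit is only a clarification.
- Hypernatremia: Grade 3 155-159, or else keep 154 in Grade 3 only. The protocol does not show which side was meant.
- Hyponatremia: Grade 1 from 130 to below the lower limit of normal.
- BUN, AST, ALT, GGT and alkaline phosphatase: Grade 2 >2.5 to 5.0 and Grade 3 >5.0 to 10 x ULN.
- Hyperthyroidism: in Grade 3, replace the need for medication by lack of control despite it, as the hypothyroidism row does.
- Intermenstrual bleeding: Grade 3 strictly more than a typical cycle.

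Clinicians should confirm the last two. The cost is a few table cells and the matching re-grading code, with no extra data, visits or subjects.
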